# 1 Background and Rationale

[figure not shown]
## 1.1 Barrett's Esophagus

Barrett's esophagus (BE) is a common premalignant condition associated with gastroesophageal reflux disease (GERD). [1, 2] About 10% of patients with chronic GERD develop BE, which has an overall estimated prevalence of 1.6% in the general population. [3, 4] BE is characterized by replacement of normal squamous epithelium by columnar epithelium with goblet cells, otherwise known as intestinal metaplasia.[5] It is associated with an increased risk of esophageal adenocarcinoma, but the rate of progression to malignancy varies depending upon histologic findings. Risk of malignant transformation is up to 10% per year in patients with high grade dysplasia. [6-7]

## 1.2 Endoscopic Eradication Therapy

Endoscopic eradication therapy (EET) is a term used to describe various endoscopic modalities employed to eradicate dysplastic lesions in Barrett's esophagus, including endoscopic mucosal resection (EMR), endoscopic submucosal resection (ESR), radiofrequency ablation (RFA), photodynamic therapy (PDT), and cryoablation. EET reduces the risk of disease progression to higher grade dysplasia and to adenocarcinoma in patients with BE and dysplasia. [1, 8]. EET is also cost effective when compared to surveillance alone. [9] EMR can be used alone for curative intent of dysplastic BE or prior to RFA with lesions identified on EMR. EMR followed by RFA is currently the treatment of choice for patients with BE and high grade dysplasia, as eradicated rates are improved compared with treatment with either modality alone. [10] Given these data, it is especially important to maximize the identification of all visible BE lesions.

Figure 1: Endoscope with cap attached

Transparent fitted cap endoscopy can be used to increase diagnostic and therapeutic yield in a variety of settings including screening colonoscopy, esophageal foreign body retrieval, and GI bleeding. [11-15] In screening colonoscopies for example, caps increase the diagnostic yield of detecting polyps by 5-10%. [11, 12] In the setting of this proposed study, caps may improve visualization and detection of mucosal abnormalities through a variety of mechanisms, including keeping mucosa within range of the focal depth of the endoscope, stabilizing the endoscope, and helping to align a target lesion for biopsy and/or therapy. A previous study assessing the effect of cap-assisted endoscopy in diagnosing BE in a population with suspected disease increased the probability of diagnosis from 69.4% to 83.3% when compared to conventional endoscopy. [15] However to date, the utility of cap assisted endoscopy in detecting visible and dysplastic lesions in BE has not been evaluated.

### **1.3 Rationale**

Our hypothesis is that the addition of a transparent cap to the end of the endoscope will increase the detection and diagnostic yield of visible lesions in Barrett's esophagus. Thus, the goal of this tandem design trial is to compare the diagnostic yield (DY) of cap assisted endoscopy with that of conventional endoscopy using high definition-white light endoscopy (HD-WLE) and narrow band imaging (NBI) in patients with Barrett's esophagus.

## **2 Objectives**

### **2.1 Primary Objective**

To compare the diagnostic yield of esophagogastroduodenoscopy (EGD), a test to examine the lining of the esophagus, stomach, and first part of the small intestine, with HD-WLE and NBI with the diagnostic yield of cap-assisted EGD with HD-WLE and NBI. "Diagnostic yield" is defined as the proportion of EGD in which visible BE lesions were identified and confirmed histologically as low grade dysplasia, high grade dysplasia, intramucosal cancer, or invasive adenocarcinoma

### **2.2 Secondary Objectives**

1. To determine the number of visible lesions detected per person in EGD with vs without cap.
2. To evaluate the detection of high grade dysplasia and esophageal adenocarcinoma in EGD with vs without cap
3. To determine the total procedure duration in minutes
4. To assess safety by recording procedure-related adverse events.

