### 5.2 Intervention

After randomization, the endoscopist will then perform exam with or without cap using HD-WLE and NBI and identify visible lesions. Identified lesions will be recorded on the case report form using a blank clock face divided in four quadrants and with distance from the incisors in cm. The endoscope will then be withdrawn. A second endoscopist will then perform a second EGD with a cap if none was used on initial exam or without a cap if one was used on initial exam. The second endoscopist will be blinded to the results of the initial exam. If there is no physician available to perform second endoscopy then the patient will not be considered for the study. Visible lesions will be recorded in same format as initial exam. Finally, the endoscopist of record will biopsy or perform EMR of all noted lesions, which will be sent for pathological review, the results of which will be captured from the medical record. All procedures will be performed by a gastroenterologist experienced in EET or by a fellow under direct supervision. Patients will be contacted in 48 hours by phone by clinical staff to monitor for AEs

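### Secondary objective 1 counts visible lesions without histology, so it cannot tell better detection from more marking, and no endpoint explicitly counts confirmed lesions per exam

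*Combined protocol and SAP*

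**What the plan says.** Section 2.2 lists four secondary objectives. The first is "To determine the number of visible lesions detected per person in EGD with vs without cap". The second is "To evaluate the detection of high grade dysplasia and esophageal adenocarcinoma in EGD with vs without cap", and it does not say whether the unit is the patient, the exam or the lesion.

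Section 2.1 defines the primary measure, diagnostic yield, in these words: "the proportion of EGD in which visible BE lesions were identified and confirmed histologically as low grade dysplasia, high grade dysplasia, intramucosal cancer, or invasive". The last item in that list is adenocarcinoma. Each EGD therefore scores yes or no.

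Section 5.2 sets out what is recorded and who knows what:
- "Identified lesions will be recorded on the case report form using a blank clock face divided in four quadrants and with distance from the incisors". No criterion is given for what qualifies as a lesion.
- "A second endoscopist will then perform a second EGD with a cap if none was used on initial exam or without a cap". The latter applies when the first exam was done with the cap. The operator therefore works with known cap status.
- "The second endoscopist will be blinded to the results of the initial exam". This is the only blinding described. It concerns the first exam's findings, not the cap.
- "the endoscopist of record will biopsy or perform EMR of all noted lesions, which will be sent for pathological review".

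Section 1.3 states the hypothesis that the cap raises both the detection and the diagnostic yield of visible lesions. Section 9.2 gives generic tests only (chi-square, Student's t, Wilcoxon rank-sum). It plans no count of confirmed lesions and no proportion of noted lesions confirmed by method.

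**The concern.** Objective 1 is the only endpoint stated as a number of lesions, and the only detection endpoint not tied to a histological diagnosis. It depends on the judgement of operators who know the cap status, under a hypothesis that points one way. A higher count with the cap could mean more neoplasia found, more harmless tissue marked, or both, and the count alone cannot say which.

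The primary endpoint does not fill the gap. Suppose a patient has three dysplastic lesions, of which one is seen without the cap and all three with it. Both exams score yes, and the patient contributes no difference. Section 1.2 nevertheless motivates the trial with "Given these data, it is especially important to maximize the identification of all visible BE lesions". A real gain in patients with several lesions would be invisible in the primary and mixed with any unconfirmed marks in objective 1. A statement that the cap finds more lesions per person could then rest on extra sampling of non-neoplastic tissue, since every noted lesion is biopsied or resected.

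**Working it through.** **What each detection endpoint can show**

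| Endpoint | Histology required | Counts lesions | Range of diagnoses |
|---|---|---|---|
| Primary (2.1) | yes | no, yes/no per EGD | LGD, HGD, intramucosal and invasive cancer |
| Secondary 1 (2.2) | no | yes, per person | any visible lesion |
| Secondary 2 (2.2) | yes, by its diagnoses | unit not stated | HGD and adenocarcinoma only |

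No row explicitly combines histology, a lesion count and the full range including LGD.

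**Size of the effect if over-marking occurs**

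The plan gives no effect size or power for objective 1, so there is no figure of its own to reproduce. From the documents I take only the 170 patients (section 9.1). All rates below are assumptions.

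- True lesions per patient: Poisson with mean 0.625.
- Each is seen with probability 0.8, independently in each exam and equally with and without the cap. Each exam then finds 0.625 × 0.8 = 0.5 true lesions on average, so there is no true difference.
- Unconfirmed marks per exam: Poisson, 0.5 without the cap and m with it.

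The mean difference in visible count is m − 0.5.

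*Paired test.* The variance of the within-patient difference is 2 × 0.625 × 0.8 × 0.2 + 0.5 + m = 0.7 + m.
- m = 0.7: SE = √(1.4/170) = 0.0907; 0.2/0.0907 = 2.20; Φ(2.20 − 1.96) ≈ 0.60.
- m = 0.8: SE = √(1.5/170) = 0.0939; 0.3/0.0939 = 3.19; Φ(3.19 − 1.96) ≈ 0.89.

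*Unpaired t test, as section 9.2 reads.* The test's own variance is 2 × 0.625 × 0.8 + 0.5 + m = 1.5 + m, while the difference still varies with the paired SE.
- m = 0.7: threshold 1.96 × √(2.2/170) = 0.223; Φ((0.2 − 0.223)/0.0907) ≈ 0.40.
- m = 0.8: threshold 1.96 × √(2.3/170) = 0.228; Φ((0.3 − 0.228)/0.0939) ≈ 0.78.

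Simulation agrees: about 59% and 89% paired, and about 39% and 78% unpaired. At m = 0.6 the figures are about 21% and 9%. At m = 1.0 both exceed 99%.

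*Confirmed-lesion count, paired test.* If no mark is dysplastic, the expected difference is zero and the count significantly favours the cap in about 2.5-3% of trials (about 5% two-sided). If 20% of marks prove dysplastic, the difference is 0.2 × (m − 0.5) and the variance is 0.2 + 0.2 × (0.5 + m).
- m = 0.7: 0.04/√(0.44/170) = 0.79; Φ(0.79 − 1.96) ≈ 0.12.
- m = 0.8: 0.06/√(0.46/170) = 1.15; Φ(1.15 − 1.96) ≈ 0.21.

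*Proportion confirmed, if no mark is dysplastic.* Without the cap it is 0.5/(0.5 + 0.5) = 50%. With the cap it is 0.5/1.2 = 42% at m = 0.7 and 0.5/1.3 = 38% at m = 0.8. This measure exposes the over-marking that the visible count hides.

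**Sensitivity to lesion density** (visible count, m = 0.7 and 0.8)

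| True lesions per patient | Paired | Unpaired |
|---|---|---|
| 0.5 | 60%, 89% | 43%, 81% |
| 1 | 56%, 87% | 30%, 67% |
| 2 | 47%, 82% | 15%, 43% |

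**The case against.** **The bias is conditional.** A reader might infer that the cap will lead operators to mark harmless tissue. The documents do not say so. Section 1.2 instead gives mechanisms for truly better visualisation. The simulation assumes extra marks and then counts them, so it shows what the endpoint would do with over-marking and is not evidence that over-marking will happen. This stands.

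**Counting visible lesions is a legitimate aim.** Section 1.3 names detection of visible lesions beside diagnostic yield, so objective 1 is not at odds with the rationale. This stands, and is a reason to keep the count as a descriptive measure.

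**Confirmed disease is not ignored.** A reader might infer that nothing else in the plan reflects confirmed lesions. Objective 2 names histological diagnoses and, with its unit unstated, could be read per lesion. The gap is the narrower one: no explicit count of confirmed lesions including LGD.

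**The main result is protected.** An unconfirmed mark cannot by itself raise the primary endpoint or objective 2. This stands, and limits the point to a secondary objective.

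**Histology is not a complete remedy.** Patients are enrolled for confirmation or treatment of dysplasia (section 3.1), so some extra marks may prove dysplastic through more sampling alone. This stands, as the 12% and 21% figures show.

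**The change costs more than wording, because lesions must be linked to pathology.** This does not stand. The primary endpoint already needs each exam's noted lesions linked to their histology.

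**Conclusion.** The point holds as a limit on what objective 1 can support. As defined, it cannot separate better detection from more marking, and no other endpoint explicitly supplies a confirmed-lesion count per exam. Under the assumed rates, 0.2 extra unconfirmed marks per cap exam (one per five patients) would give a significant result for the cap in about 59% of trials with a paired test, or about 39% with the unpaired t test, with no true difference in detection. At 0.3 extra marks the figures are about 89% and 78%. They depend on assumed mark rates and lesion density and are not predictions. The documents do not support the stronger readings that over-marking will occur or that the primary endpoint is compromised. The change is worth making because it uses data the trial already collects and sharpens what can be concluded.

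**What to change.** - In section 2.2, make the tested lesion-level comparison the number of histologically confirmed lesions (LGD, HGD, intramucosal cancer, invasive adenocarcinoma) per exam, with versus without cap.
- Keep the visible-lesion count as a descriptive measure. Report beside it the proportion of noted lesions confirmed for each method.
- In section 9.2, name the confirmed-lesion analysis and state that it uses the same lesion-to-pathology linkage as the primary endpoint, through the recorded clock-face position and distance.
- As an optional addition, state beforehand what qualifies as a visible lesion. That acts on the cause, which histology does not.

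The cost is wording in two sections, with no new procedure or data. The drawbacks are smaller counts, and that histology reduces over-marking bias without eliminating it.

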## **3 Eligibility Criteria**

### **3.1 Inclusion Criteria**

1. Must be at least 18 years of age.
2. Must be patients undergoing standard of care EGD for the confirmation of dysplasia in BE or EET for dysplasia in BE.
3. Must be able to understand and willing to sign an IRB-approved written informed consent document.

### **3.2 Exclusion Criteria**

1. Pregnant or breastfeeding.
2. Prior endoscopic treatment for BE.
3. Unable to tolerate sedation due to medical comorbidities.

### **3.3 Inclusion of Women and Minorities**

Both men and women and members of all races and ethnic groups are eligible for this trial.

## **4 REGISTRATION PROCEDURES**

**Patients must not start any protocol intervention prior to registration through the Siteman Cancer Center.**

The following steps must be taken before registering patients to this study:

1. Confirmation of patient eligibility by Washington University
2. Registration of patient in the Siteman Cancer Center database
3. Assignment of unique patient number (UPN)

Once the patient has been entered in the Siteman Cancer Center OnCore database, the WUSM coordinator will forward verification of enrollment and the UPN via email.

#### **4.1 Confirmation of Patient Eligibility**

Confirm patient eligibility by collecting the information listed below and scanning and emailing it to the research coordinator at least one business day prior to registering patient:

1. Your name and contact information (telephone number, fax number and email address)
2. Your site PI's name, the registering MD's name, and your institution name
3. Patient's race, sex, and DOB
4. Three letters (or two letters and a dash) for the patient's initials
5. Current approved protocol version date
6. Planned date of enrollment
7. Completed eligibility checklist, signed and dated by a member of the study team
8. Copy of appropriate source documentation confirming patient eligibility

#### **4.2 Patient Registration in the Siteman Cancer Center OnCore Database**

Registrations may be submitted Monday through Friday between 8am and 5pm CT. Urgent late afternoon or early morning enrollments should be planned in advance and coordinated with the Washington University research coordinator. Registration will be confirmed by the research coordinator or his/her delegate by email within one business day. Verification of eligibility and registration should be kept in the patient chart.

All patients at all sites must be registered through the Siteman Cancer Center OnCore database at Washington University.

#### **4.3 Assignment of UPN**

Each patient will be identified with a unique patient number (UPN) for this study. Patients will also be identified by first, middle, and last initials. If the patient has no middle initial, a dash will be used on the case report forms (CRFs). All data will be recorded with this identification number on the appropriate CRFs.

#### **4.4 Randomization**

Consenting and eligible participants will be randomized to one of two arms. Participants in the first arm will undergo EGD with cap first, followed by EGD without cap. Participants in the second arm will undergo EGD without cap first, followed by EGD with cap. All participants will have EGD with and without cap; the randomization affects the order in which the procedures take place. The order of cap placement will be determined by a preprinted randomization sequence kept in an opaque envelope that will be opened after enrollment.

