### 6.1 Definitions

#### 6.1.1 Adverse Events (AEs)

**Definition:** any unfavorable medical occurrence in a human subject including any abnormal sign, symptom, or disease.

**Grading:** the descriptions and grading scales found in the revised NCI Common Terminology Criteria for Adverse Events (CTCAE) version 4.0 will be utilized for all toxicity reporting. A copy of the CTCAE version 4.0 can be downloaded from the CTEP website.

**Attribution (relatedness), Expectedness, and Seriousness:** the definitions for the terms listed that should be used are those provided by the Department of Health and

Human Services' Office for Human Research Protections (OHRP). A copy of this guidance can be found on OHRP's website: <http://www.hhs.gov/ohrp/policy/advevntguid.html>

Risks associated with this study include risk of breach of confidentiality and having to be under sedation for an additional 2-5 minutes while the second exam of the study is being performed.

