### **9.2 Analysis methods**

This study will collect both categorical and quantitative demographic variables and endoscopy procedural details: procedure duration, diagnostic findings, and procedure complications. Pathology results will be recorded and the electronic medical record will be reviewed to extract any relevant clinical information. All complications will be noted. All information will be transferred into a database. The categorical variables will be summarized using frequencies and percents, while the quantitative variables will be summarized using means and standard deviations. Chi square test will be used for categorical variables while student's t test will be used for quantitative variables to test the difference between the study groups. Additionally, multivariable analysis will be used in order to identify factors associated with success increasing diagnostic yield. Continuous variables with a non-normal distribution will be compared using the Wilcoxon rank-sum test. The statistical software program SPSS will be used for analysis. A two sided p value of < 0.05 will be considered significant.

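### Exam order is the only randomised factor, yet section 9.2 names no within-patient model with an order term and no first-exam comparison

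*Combined protocol and SAP*

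**What the plan says.** Section 4.4 (Randomization): "Consenting and eligible participants will be randomized to one of two arms", one with the cap exam first and one with the cap exam second. "All participants will have EGD with and without cap; the randomization affects the order in which the procedures take place". The section gives no allocation ratio and no blocking.

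Section 5.2 (Intervention): after exam 1, "The endoscope will then be withdrawn". Then "A second endoscopist will then perform a second EGD with a cap if none was used on initial exam", and the reverse if a cap was used. "The second endoscopist will be blinded to the results of the initial exam". Sampling comes after both exams: "Finally, the endoscopist of record will biopsy or perform EMR of all noted lesions". Examiners may be gastroenterologists experienced in eradication therapy or supervised fellows. The section does not say how examiners are allotted to exam 1 and exam 2.

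Section 6.1.1 confirms that the exams share one sedation, listing as a risk "having to be under sedation for an additional 2-5 minutes while the second exam of the study is being performed".

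Section 9.2 (Analysis methods) compares what it calls study groups, without defining them: "Chi square test will be used for categorical variables while student's t test will be used for quantitative variables to test the difference between the" (the sentence ends by naming those groups). A Wilcoxon rank-sum test is named for non-normal variables. A multivariable analysis of factors associated with yield is planned, but its covariates are not listed. Order, period, sequence and first-exam yield are not mentioned.

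**The concern.** The primary objective (section 2.1) compares cap with no cap, and every patient has both. Study groups in section 9.2 can be read in two ways. If they are the two arms of section 4.4, then over both exams each arm has one cap and one no-cap exam per patient, and comparing them does not estimate the cap effect. If they are the cap and no-cap exams, the named tests treat paired results as independent and ignore the order.

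Order may matter here without any carry-over, because exam 2 always has a different examiner and comes later in the same sedation. Randomising the order cancels a common exam-2 effect in the pooled estimate only when the two sequences are of equal size. Even then the effect stays in the error unless the model contains it. The trial creates a randomised factor that could deal with this, and the plan does not say that it will be used.

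**Working it through.** **The plan's own figure.** Section 9.1 gives 170 patients for a 15% increase in yield, 80% power and two-sided alpha 0.05. These inputs alone do not yield 170, because no baseline yield or discordant share is stated. Reading 15% as 15 points (an assumption), the unpaired formula gives 170 per condition for 35% to 50% or 50% to 65%. McNemar's formula gives 166 to 173 for a discordant share of 0.48 to 0.50. Neither calculation involves order.

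**Notation.** τ is the cap effect, π the exam-2 (order and operator) effect, Lc and Ln the carry-over after a cap and a no-cap exam, and s the share of patients having the cap first. The expected cap minus no-cap differences are:
- cap first: τ − π − Lc
- no cap first: τ + π + Ln

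**Order effect, no carry-over.** The pooled difference is s(τ − π) + (1 − s)(τ + π) = τ + π(1 − 2s).
- s = 0.50: no shift.
- s = 0.45: 0.5 points for π = 5, 1.0 point for π = 10.
- s = 0.40: 1.0 point for π = 5, 2.0 points for π = 10.

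Under simple randomisation of 170, s has standard deviation 0.5/√170 = 0.038, so 95% of splits lie within about 0.5 ± 0.075. The shift is then at most about 0.15π, that is 0.75 or 1.5 points. It averages to zero over repeated randomisations but not for the split that occurs. An order term removes it, because (τ − π)/2 + (τ + π)/2 = τ whatever the split.

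**Error.** The variance of the per-patient difference is the discordant share minus τ². With τ = 0.15 and a discordant share of 0.49 it is 0.49 − 0.0225 = 0.4675. With equal sequences the order effect contributes π²: 0.0025 for 5 points (0.5%) and 0.01 for 10 points (2.1%). With a discordant share of 0.25 the variance is 0.2275, and these become 1.1% and 4.4%.

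**Carry-over, if it existed.** With s = 0.5 the pooled difference is τ − (Lc − Ln)/2. For a true 15 points, a differential of +5 or +10 gives 12.5 or 10, and −5 or −10 gives 17.5 or 20. Equal carry-over gives no shift. The 5 and 10 are illustrations and are not in the documents.

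**First-exam comparison.** It is free of carry-over. Assuming 85 per arm, the 95% half-width is 1.96√[(p0(1 − p0) + p1(1 − p1))/85]:
- 40% v 55%: 1.96√(0.4875/85) = 14.8 points
- 50% v 65%: 1.96√(0.4775/85) = 14.7 points
- 60% v 75%: 1.96√(0.4275/85) = 13.9 points

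Power for 15 points is 51-64% at no-cap yields from 20% to 69.4%.

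**Can it test for carry-over?** The first-exam estimate minus the pooled estimate equals half the difference between arms in mean per-patient total, with expectation (Lc − Ln)/2. At 50% v 65% and within-patient correlation r, the variance of the total is 0.4775 + 2r√(0.25 × 0.2275).
- r = 0: SD 0.691, SE of the gap ½ × 0.691 × √(2/85) = 5.3 points.
- r = 0.7: SD 0.901, SE 6.9 points.

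With no carry-over at all, a gap above 5 points would arise by chance in about 35-47% of trials. Power to detect a 10-point differential is 11-16%, and about 30-39 points are needed for 80%.

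**The case against.** A reader might infer that the cap effect is biased by unequal carry-over. The documents do not support that. No section reports marks, oozing or hidden lesions after a first exam. Section 1.2 describes how a cap helps during an exam, not what it leaves behind. Section 5.2 closes the two main routes: a different, blinded examiner does exam 2, and tissue is taken only after both exams. Blinding to results does not hide physical traces on the mucosa, so the possibility remains, but only as a possibility.

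A reader might also infer that the plan cannot detect such an effect. That goes too far. Arm and per-exam findings are recorded, and the multivariable analysis of section 9.2 does not exclude order. What is missing is a pre-specified use of it. Nor is the absence of a washout a fault, since it is inherent in a same-sedation tandem exam.

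The objection is strongest on remedies. The cap effects in the two arms differ by 2π + Lc + Ln, which does not isolate Lc − Ln. With π = 5 and no carry-over, a true 15 appears as 10 and 20. With equal arms, an additive order term does not remove carry-over bias. A gap between the first-exam and pooled estimates is mostly noise at 170 patients. All of this stands, and it rules out a carry-over pretest or any rule that lets such a gap change the conclusion.

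It does not answer the narrower point. The named tests ignore both the pairing and the only randomised factor.

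**Conclusion.** The concern holds as a modest omission that is almost free to repair. Section 9.2 does not define the study groups, names only unpaired tests, and uses exam order in no named analysis, although order is randomised and tied to a change of examiner.

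An assumed order effect of 5 to 10 points would shift the pooled estimate by 0.5 to 2 points at splits of 45/55 to 40/60 and not at all at 50/50. Leaving it out of the model would add about 0.5-4% to the variance of the within-patient difference. Differential carry-over remains a possibility that the documents neither show nor exclude, and half of any differential would pass into the pooled effect.

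These sizes rest on assumed order effects, carry-over values, yields and discordant shares, on an assumed 85/85 split for the first-exam figures, and on reading 15% as points. The finding about the text of section 9.2 rests on none of them.

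**What to change.** In section 9.2:

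- (a) Define the primary comparison as cap versus no-cap exam within patient. Analyse diagnostic yield with a within-patient model containing cap status and exam order (first or second), for example conditional or mixed logistic regression or a period-adjusted McNemar-type test.
- (b) Pre-specify a supporting, descriptive comparison of first-exam diagnostic yield between the two randomised arms, with its 95% CI, reported beside the primary result.
- (c) State that the pooled within-patient estimate stays primary, and that neither a carry-over pretest nor cap effects by arm will be used to change the conclusion.

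The cost is wording and slightly more analysis work. No new patients, procedures or data are needed, since the randomised order is known and section 5.2 already records each exam's lesions. The downside is that the supporting estimate is imprecise, and the report should say so.
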